1.2. Schema

Figure 1. Study Schema

Study design, detailing the randomization of participants into two arms: the Phenserine Arm (n=12) and the Donepezil Arm (n=4). Participants in the Phenserine Arm will start at 5 mg twice daily (BD) with dose escalations at specified intervals up to 10mg three times daily (TDS).

Figure 2. FDA Framework for Pre-Clinical and Clinical AD

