Several steps have been taken to ensure safety and tolerability, including a) slow stepwise titration, b) divide the daily dose into three doses eg highest single dose is still 10mg, which reduces Cmax which is the main driver of side-effects, c) ensure IMP is taken with food, and d) frequent in-clinic visit with physical examination and safety laboratory measurements. Any participant who escalates to the highest allowed dose and subsequently experiences intolerable adverse effects will be down titrated to their prior dose level. If more than 2 participants experience dose-limiting side effects at the 10 mg tds dose level, no additional participants will be allowed to dose escalate to that level, and the highest dose that all subsequent participants will be allowed to reach is 10 mg bd.

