4.2. Scientific Rationale for Study Design

The randomized, controlled design is required to fully understand the safety and efficacy of phenserine in this cohort. Eligibility requires MCI or mild dementia due to AD based on biomarker confirmation. To ensure safety, the design implements drug titration at different time-points after a detailed unblinded safety-review by the DSMB. The DSMB's role will focus on overall participant safety. Individual dose titration decisions will be made by the site study clinician and Principal Investigator (PI), based on pre-defined criteria. The outcomes include exosome biomarkers, detailed cognitive testing, as well as ADL and fluid biomarker changes.

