6.6. Dose Modification

As shown in the Study Schema (Figure 1), participants randomized to the phenserine arm will initiate dosing at 5 mg bd and maintain this dose for the first two weeks of study treatment. At the Week 3 visit, participants may be escalated to 10 mg bd, then 10mg tds (Figure 1), based on tolerability, including adverse events, clinical assessment, ECG and safety laboratory measurements. Participants who are unable to tolerate a higher dose will have their dose reduced to the next previous dose level and maintained at that dose through the remainder of the study. This clinical decision will be made by the study physician and the study team at each centre at the visit, or when any safety laboratory results are received during the days after the visit. If needed, the medical monitor and the PI will be contacted. All participants are expected to be at their individualized maintenance dose for 4 weeks (beginning of Week 5 through the end of Week 8).

Participants randomized to the donepezil arm, will initiate dosing at 5 mg od and will be evaluated at the Week 4 visit for dose escalation to 10 mg once daily. For participants in the phenserine arm, dosing will follow a stepwise escalation to ensure safety and efficacy:

- **Weeks 1-2:** Participants will begin with 5 mg twice daily (bd).
- **Weeks 3-4:** Participants will escalate to 10 mg twice daily (bd) if the initial dose is well tolerated.
- **Weeks 5-8:** Participants will further escalate to 10 mg three times daily (tds) based on continued tolerability.

Before any dose escalation, the dosage will be reassessed based on tolerability. If necessary, participants may be required to return to the center for a dose reduction. Throughout the study, dose adjustments will be made according to tolerability. Should any dose escalation lead to adverse effects that compromise the participant's well-being or safety, the dose will be reduced to the previously well-tolerated level. Participants will then continue at this adjusted dose for the remainder of the study period. These procedures are outlined in more detail in the dedicated SOP.

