9.18. Pharmacokinetics

- Plasma PK samples will be collected at W 2, 4, 6, and 8 visits for all IMP participants. Samples will be analyzed for phenserine to determine C_{max} and t_{1/2}. Available data will be analyzed by the DSMB to assess the safety of ongoing patients. PK samples will also be collected at the Week 8 visit, at peak dose, from all other patients (and at the final maintenance dose level for those who down-titrate due to tolerability) prior to taking the

morning dose, to establish steady-state concentration and stored for later analyses aimed at exploring the relationship between exposure and tolerability/efficacy outcomes.

- Instructions for the collection and handling of biological samples will be provided by the sponsor. The actual date and time (24-hour clock time) of each sample will be recorded. Samples will be used to evaluate the pharmacokinetics (PK) of phenserine. Each sample will be divided into aliquots as described in the SOP. These samples may also be used to evaluate safety or efficacy aspects related to concerns arising during or after the study.

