[name] is the Chief Investigator and will have academic oversight of the trial and be responsible for reporting to the funder. The Coordinating Investigator for the PATH-1 RCT is [name], who will have overall responsibility for the conduct of the trial and interactions with the sponsor, regulator, and ethics committee, as appropriate and required during the course of the trial. [name] will be responsible for the analysis of exosomes, the primary outcome measure.

This trial will be managed by a Trial Management Group (TMG), which will include the Principal Investigators, the Trial Manager and a patient representative. The TMG will be co-chaired by the Chief Investigator and the Coordinating Investigator. The group will meet at three-month intervals and additionally as appropriate. The TMG will have direct oversight of and responsibility for the study. The remit of the TMG will also include overall progress of the trial and to monitor progress against milestones. Any discrepancy from milestones will be highlighted and a plan developed to address any difficulties. The day-to-day management of the trial will be conducted by the Trial Manager, who will report to the Coordinating Investigator on a regular basis. The Trial Manager will send a written report to the chairs of the TMG before each TMG meeting, detailing progress. Any non-urgent major decisions will be made by the TMG.

The Trial Steering Committee (TSC), , will meet twice over the course of the study (with additional meetings convened if requested by the Data and Safety Monitoring Board (DSMB) and will be responsible for oversight of trial governance and reporting to the sponsor.

A DSMB chaired by [name] (Geriatrician) will provide independent review of unblinded safety data collected during the study. All serious adverse events (SAEs) will be reviewed by the chair within 24 hours, and summary trial reports will be reviewed by the full committee every three months through its completion. The data will be prepared for these reviews by a separate team of unblinded data managers and statisticians who have no involvement in the day-to-day conduct of the study.

The committee will be governed by a charter and will make recommendations to stop, continue or modify the trial based on their ongoing review of the safety data. Emergency meetings will be convened on an ad hoc basis and as warranted by emergent study data.

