11.1.2. Recruitment strategy

Clinical trial recruitment will be conducted at 6 clinical trial centers. The centers have established track records for successful recruitment. The PIs have worked together on successful clinical cohort and clinical trial studies for more than 15 years and have an excellent record of successful collaboration.

The usual recruitment approach will be supplemented by the PROTECT Norge platform an online cohort study that supports nested clinical trials. It is coordinated as a partnership between the University of Exeter and University Hospital Stavanger. PROTECT Norway currently has more than 5,000 participants over 50 years of age without dementia, including more than 600 participants with stage 2 or stage 3 MCI and is continuing to actively recruit additional participants. Appropriate individuals may be invited to participate as PROTECT has the advantage of recruiting from a population with an established trajectory of cognitive decline and from the specific population on which the power calculations are based.

The expected enrolment period is ~3 months from the first patient to last patient randomised. Based on the 8-week treatment period and safety follow-up period for the last patient in, the full

duration of the study is expected to be ~6 months. Recruiting participants from high quality and experienced clinical trial centers will maximize inter-rater reliability. Each center has active memory clinics, research cohorts of people with MCI and active clinical trial programs, further supplemented by PROTECT recruitment as needed.

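### The cap on escalation to 10 mg tds is not assured to act in time: dose-limiting is undefined, the cross-site count has no owner, and the review schedule is inconsistent

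*Protocol*

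**What the plan says.** Section 2.3.1 of the protocol (Risk Assessment) sets a cap: "If more than 2 participants experience dose-limiting side effects at the 10 mg tds dose level, no additional participants will be allowed" to escalate to it, and later participants stop at the level below.

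The sections a site works from do not repeat the cap. Sections 4.4.4 and 6.3 leave escalation to individual tolerability, and section 7.1 gives individual stopping criteria. Section 6.6 says of dose changes: "This clinical decision will be made by the study physician and the study team at each centre at the visit", or when laboratory results arrive later. The medical monitor and PI are contacted only if needed.

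On oversight, section 4.2 says: "To ensure safety, the design implements drug titration at different time-points after a detailed unblinded safety-review by the DSMB". It then describes the DSMB's role as overall participant safety and leaves individual titration to the site clinician and PI. Section 9.18 says, of PK sampling: "Available data will be analyzed by the DSMB to assess the safety of ongoing patients". Section 11.1.1 (Trial management) says that "summary trial reports will be reviewed by the full committee every three months through its completion", adds chair review of every SAE within 24 hours, and allows ad hoc emergency meetings. SAP section 10 refers to ongoing review by the medical monitor and DSMB according to protocol.

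On scale, section 1.2 gives 12 phenserine and 4 donepezil participants. Section 11.1.2 says "Clinical trial recruitment will be conducted at 6 clinical trial centers" and "The expected enrolment period is ~3 months from the first patient to last patient randomised"; the synopsis (section 1.1) gives a 6-month enrolment period.

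**The concern.** A rule that counts across participants needs four things: a definition of what is counted, someone who counts, a route by which cases reach that person, and a way to tell sites when the count is reached. The protocol and SAP supply none of these for the cap. A centre following sections 4.4.4, 6.3 and 6.6 could keep escalating after the third affected participant has appeared elsewhere.

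The expected side effects make this more likely. Section 2.2 names nausea, vomiting and diarrhoea as the commonest, and section 2.3.1 handles intolerance at the top dose by down-titration. Such a case can be dose-limiting without being an SAE, and the 24-hour route covers SAEs only.

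The analysis is also affected. SAP section 3.4.2 treats a dose that does not follow the protocol's escalation rules as a major deviation, and such participants may be excluded from analysis populations. A site unaware that the cap had been reached could cause such a deviation without knowing it.

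**Working it through.** The plan states no dose-limiting rate, trigger probability or reaction time for the cap, so there is no figure of its own to reproduce.

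**Step 1. Can one centre see the trigger?** 12 phenserine participants / 6 centres = 2 per centre on average. The trigger is 3 or more, so an average centre cannot observe it alone.

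**Step 2. Calendar.** Assumptions: even accrual over E weeks (13 or 26), tds decision at Week 4, end of treatment at Week 8, and DSMB reviews 13 and 26 weeks after recruitment opens. Section 11.1.1 does not say when the three-month clock starts.

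| Quantity | E = 13 | E = 26 |
|---|---|---|
| Past Week 4 at week 13: 12 × (13 − 4)/E | 8.3 | 4.2 |
| Finished treatment at week 13: 12 × (13 − 8)/E | 4.6 | 2.3 |
| Past Week 4 at week 26 | 12 (last decision at 13 + 4 = week 17) | 12 × (26 − 4)/26 = 10.2 |

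With 3-month enrolment, only one scheduled review falls before the last escalation decision.

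**Step 3. How likely is the trigger?** If all 12 escalate and each has probability p of a dose-limiting effect,

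P(3 or more) = 1 − [(1 − p)^12 + 12p(1 − p)^11 + 66p²(1 − p)^10].

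The documents give no such rate. Section 2.3.1 reports figures for 15 mg twice daily, the same 30 mg daily total, that serve only to span a range: 5.9% withdrawals for adverse events, 11% vomiting, 19% nausea. The 30% row is a pure assumption.

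| p | P(3 or more of 12) |
|---|---|
| 5.9% | 3.0% |
| 11% | 13.8% |
| 19% | 40.6% |
| 30% | 74.7% |

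For p = 19%, the bracket is 0.0798 + 0.2245 + 0.2897 = 0.594, and 1 − 0.594 = 0.406.

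**Step 4. What does delay cost?** A simulation (40,000 runs per scenario) drew enrolment times uniformly, let all 12 escalate at Week 4, and had dose-limiting effects picked up at Week 6 or Week 8 with equal chance. The table shows, among runs with 3 or more affected, the share in which the cap acts while at least one participant has not yet escalated.

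| Enrolment | Action | p = 19% | p = 30% | p = 50% |
|---|---|---|---|---|
| 3 months | live count | 49% | 62% | 86% |
| 3 months | quarterly review only | 20% | 30% | 55% |
| 6 months | live count | 67% | 77% | 94% |
| 6 months | quarterly review only | 46% | 58% | 80% |

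The mean number still unescalated when the cap acts is 1.5 / 2.1 / 3.5 with a live count and 0.6 / 0.9 / 1.8 with quarterly action (3 months), and 2.3 / 3.0 / 4.8 against 1.0 / 1.4 / 2.3 (6 months). Acting only quarterly cuts the number protected by about half or more.

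**Step 5. Do the oversight passages agree?** Section 4.2 places a DSMB review before titration. Section 6.6 has the centre decide at the visit. Section 9.18 has the DSMB use PK data for people still on treatment. Section 11.1.1 has a full review every three months, longer than the 8-week treatment period. SAP section 10 points back to the protocol and so adds no schedule. These cannot all describe one process unless there is a further review that neither document sets out.

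**The case against.** A reader might infer that the cap cannot work, that nobody keeps the count, and that the DSMB meets only every three months. The documents do not support that reading.

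- Section 11.1.1 provides ad hoc DSMB meetings and 24-hour chair review of SAEs, and SAP section 10 refers to ongoing review.
- Sections 4.4.4 and 6.6 delegate dose handling to SOPs, and the DSMB has a charter. These are not in the file and may name a keeper of the count. Dose reductions are recorded (section 6.5), Viedoc is described as allowing real-time reports (Appendix 5), and a Trial Manager runs the study day to day.
- Even quarterly action comes before the last escalation in 20% to 80% of triggered cases in Step 4, and a live count misses some.
- The cap limits escalation; it does not stop the study. Individual dose reduction and the stopping criteria in 7.1 remain, as do the study-level provisions in 4.6, 5.5 and 11.1.1.
- Section 4.2 goes on to leave individual titration to the site clinician and PI, so it does not clearly promise a DSMB review before each participant's step.
- At 5.9% the trigger has only about a 3% chance.

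All of this stands and limits the claim. It does not supply what is missing. An ad hoc meeting depends on someone noticing the count, SAE review does not capture non-serious dose-limiting effects, and a count cannot be consistent while the term is undefined.

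**Conclusion.** The concern holds in this form: the only numeric cross-participant safety rule is not assured to act in time. It has no definition of dose-limiting, no assigned owner, no reporting route for non-serious cases and no place in the working sections, and the passages on DSMB review do not agree. The effect is delay, not certain failure. With 3-month enrolment about 8 of 12 have passed the Week 4 decision by a week-13 review, and with 6-month enrolment about 4 of 12. If the cap is triggered under 3-month enrolment, it still protects someone in 20% to 55% of cases with quarterly action, against 49% to 86% with a live count.

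These sizes rest on even or uniform accrual, all 12 escalating, assumed dose-limiting rates and an assumed DSMB clock. The textual gaps do not depend on them. The point should be fixed, but because other safeguards remain it does not leave participants unprotected.

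**What to change.** Carry the section 2.3.1 rule into sections 4.4.4 and 6.6 by cross-reference, and have the sponsor define dose-limiting. Flag each affected participant, rather than each event, in Viedoc, with prompt notification to a named central role such as the medical monitor. That role keeps the cross-site count, makes it available to sites before the Week 4 escalation decision, and informs sites and the DSMB when the count in 2.3.1 is reached.

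Reconcile protocol sections 2.3.1, 4.2, 6.6, 9.18 and 11.1.1 and SAP section 10 into one account of who reviews what, and when relative to the 8-week treatment period. If the SOPs or the DSMB charter already cover this, cite them. The threshold, the dose and the handling of participants already at that dose are for the sponsor and DSMB.

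The cost is protocol and charter wording, one eCRF flag with an alert, a small amount of monitoring work and a possible short wait at the Week 4 visit. No extra participants or procedures are needed.

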2.3.2. Benefit Assessment

There is an ongoing need to develop disease modifying therapies for AD that are well tolerated and can be widely available to people with AD. Established treatment is limited to, at best, a modest reduction in symptoms but cannot prevent continuous symptomatic deterioration and progressing neuropathology. New disease-modifying anti-amyloid drugs, which can reduce the rate of decline by 25% (14), and are likely to be available soon across Europe, but whilst they will represent an important step forward, their use will be limited by safety and cost. After an initial negative decision, a decision to approve lecanemab was recently made by EMA for lecanemab. However, the effect size is rather small, and safety issues remain, and the drug will not be available for all AD patients. It is still therefore a vital aim to develop effective disease modifying treatments that can be made available to the majority of people with AD, including older and frailer individuals who will not be suitable for the next generation of disease modifying therapies. Although phenserine was previously tested and failed to show efficacy in participants with suspected but unverified mild to moderate AD, follow-up analysis by Axonyx and others identified flaws in the trial design and study conduct that likely contributed to the lack of observed therapeutic benefit..

Although phenserine was initially developed and evaluated as a cholinesterase inhibitor (3), there are several mechanisms by which phenserine may act on neuronal and synaptic loss (15), a key common pathway evident in AD, traumatic brain injury and other neurodegenerative diseases. A range of pre-clinical studies indicate that phenserine suppresses interleukin-1b, reduces glutamate-induced excitotoxicity, protects against H₂O₂- induced oxidative toxicity, reduces A-beta levels, improves neural precursor cell viability, elevates neurotrophic brain-derived neurotrophic factor, inhibits APP and a-synuclein synthesis, (16).

Whilst these potential actions are of interest, more recent work has suggested that phenserine may confer significant neuroprotection by inhibiting apoptosis through actions on a Pre-Programmed Cell Death Pathway (17). This has been evaluated in several rodent models of neuronal loss, including APP/PSEN1 transgenic AD mice, re-perfusion injury and a weight drop mouse model of traumatic brain injury. In all of these animal studies, treatment with phenserine significantly reduced neurodegenerative lesions, and decreased the neuro-inflammatory response through IBA1 and TNF- α pathways in the hippocampi and cortices of wild type (WT) mice, and in cortices of AD mice(16–19). Synaptic density and Synaptophysin (Syn)-IR were also significantly protected in phenserine-treated AD and TBI animals (16–19).

The mechanisms underlying the protection of neurons were evaluated in cell culture and by using novel exosome technologies to examine key cell pathways from in vivo studies of anoxia and TBI (15,20). For example, Phenserine increased BDNF, Bcl-2, phosphorylated ERK-1/2, and lowered activated caspase-3 protein levels in SH-SY5Y cells exposed to OGD-hypoxia and neuronal injury (18). Despite the failure of Axonyx's previous late-phase clinical program, these new findings support further investigation of phenserine's potential therapeutic utility in AD and potentially other forms of neurodegenerative disease. With this in mind, we have optimized the study design for the PATH-1 study to enhance the study design and methodology to more thoroughly characterize phenserine's potential therapeutic properties.

2.3.3. Optimization of the PATH-1 Protocol for Assessing the Safety and Efficacy of Phenserine in People with Early or Mild AD

The design of the PATH-1 study has been optimized based on the issues identified in the previous Axonyx program (20,21), as follows:

- The eligibility criteria will more definitively identify patients with early or mild AD (based on FDA guidance and on a confirmed significant change on a validated biomarker of AD). This patient population may be more likely to respond to treatment based on a confirmed diagnosis and given the early course of their disease.
- The 6:2 randomization to phenserine or donepezil will ensure adequate early assessment of phenserine's safety and PK, while minimizing a potential placebo effect by offering the other group a well-established and generally effective treatment for people with early or mild AD.
- The titration schema and criteria for establishing a patient-specific maintenance dose will ensure that participants achieve an individually optimized dose based on safety.
- The therapeutic utility of phenserine will be evaluated using novel exosome technologies as well as other established blood- and CSF-biomarkers of AD. In addition, well-established cognitive assessments will provide further characterization of phenserine's effects on AD symptomatology. Together the results of these assessments will be used to select doses and outcome measures for a subsequent Phase 2 study of phenserine in people with early or mild AD.

2.3.4. Overall Benefit Risk Conclusion

Overall, there is strong pre-clinical evidence of phenserine's biological effects that are relevant to the treatment of AD and other neurodegenerative conditions, with a novel effect on apoptosis in addition to cholinesterase inhibition. Previous clinical trials with phenserine suggest a good clinical safety profile and offer some encouraging indications of potential benefit. The protocol has been designed based on the learnings of the failed Axonyx program and will ensure that the patient population is appropriate and that the study assessments more fully characterize phenserine's potential therapeutic utility across more robust measures of pharmacodynamic effects and any correlated improvements in cognitive function.

3. Objectives, and Endpoints

The study will be conducted as a 2 arm, parallel group, randomized RCT of phenserine compared to donepezil in people with early or mild AD. A total of 16 participants will be recruited from sites across Norway and be supported by the PROTECT platform. Eligible participants will be randomized 6:2 to phenserine or donepezil in an unblinded manner.

The end of the research active period for this study is set to January 1, 2028. All analyses within the scope of this study will be completed by this date.

The pharmacodynamic (PD), pharmacokinetic (PK), and safety data from this study are intended to inform dose selection and study design for a subsequent Phase 2 study of phenserine over a longer treatment duration in people with early to mild Alzheimer's disease (AD). The objectives of the study are as follows:

Primary Objective:

To assess the effects of phenserine compared to donepezil on exosome biomarkers of cell death in people with early or mild AD.

Key Secondary Objective:

To evaluate the safety and tolerability profile, of phenserine at ascending doses up to 10 mg tds as compared to donepezil at doses up to 10 mg od in participants with early or mild AD.

Other Secondary Objectives:

To evaluate steady state blood levels of phenserine for the purpose of characterizing and comparing dose-response relationships for pharmacodynamic outcomes and key safety assessments.

To evaluate the proportion of participants in the phenserine arm who achieve the target AChE inhibition of approximately 45%, stratified by dose regimen and the time required to reach the target AChE inhibition of ~45% and the duration participants maintain this inhibition during the treatment period.

To evaluate compliance, the study will measure the extent to which participants take the study medication according to the protocol. Compliance will be assessed using the subject diary and the registration of returned capsules.

Exploratory Objectives:

To evaluate changes in specific biomarkers of Alzheimer's Disease (AD) in cerebrospinal fluid (CSF): A β 1-40, A β 1-42, Tau, and p-tau, and in blood plasma: p-tau217 and NfL.

To assess phenserine's potential short-term effects on specific cognitive tests using the FLAME Memory Composite and other cognitive sub-tests.

To evaluate changes in overall cognitive function using the Montreal Cognitive Assessment (MoCA):

Primary Endpoint:

Changes in exosome biomarkers of pre-programmed cell death, synaptic integrity and function, neuroinflammation, and AD-related protein trafficking in participants treated with phenserine versus those treated with donepezil. Although patients and site staff will be unblinded to the treatment modality administered, they will be blinded to the results of the biomarker evaluations until the study is completed.

Key Secondary Endpoints:

Safety and tolerability of phenserine compared to donepezil in participants with early or mild AD based on the frequencies of reported or observed adverse events (AEs) and serious adverse events (SAE), vital signs, clinical laboratory evaluations, ECGs, and modified CSSRS scores.

Other Secondary Endpoints:

Pharmacokinetic parameters will be assessed at steady state for determination of dose-response relationships for phenserine and donepezil.

Evaluate the proportion of participants in the phenserine arm who achieve the target AChE inhibition of approximately 45%, stratified by dose regime and assess the time required to reach the target AChE inhibition of ~45% and the duration participants maintain this inhibition during the treatment period. Blood samples will be analyzed for Acetylcholinesterase (AChE) activity using a modified Micro-Ellman method (22) normalized to recombinant AChE enzyme activity (refer to Appendix 10).

Compliance will be recorded, based on drug count and subject diary, including the proportion of participants complying with the treatment schedule. Compliance is defined as drug intake within 80-120% of the scheduled dosing.

Exploratory Endpoints:

Assess changes in Alzheimer's Disease (AD) biomarkers in cerebrospinal fluid (CSF): A β 1-40, A β 1-42, Tau, and p-tau, and in blood plasma: p-tau217 and NfL.

Neuropsychology assessments will be conducted using the FLAME computer-based domain composites for memory, executive function, attention and sustained attention to evaluate changes over the 8-week treatment period in the phenserine treated participants compared to those who received donepezil. In addition, evaluate overall cognitive changes using the Montreal Cognitive Assessment (MoCA).

